### 8.3 Vital signs

Each Vital Sign, i.e. Weight, Height (at baseline only), BMI, Body Fat (FatM and FatP) Total Body Water, Fat Free Mass, Bone Body Mass, Metabolic Age, Visceral Fat, PAS, PAD and HR will be summarized by timepoint using descriptive summaries as described in Section 5.

All the variables will be measured across all the study visits. Changes from the Baseline Visit to all the subsequent study visits will be also generated.

Table S.3 will include the summaries of the Vital Signs by group. A listing will be also produced (Listing S.2).

### 8.4 End study information

Table S.4 (Appendix 2) will include all the information recorded in the End Study Form of the eCRF, i.e. completeness of the study and frequency table of the reasons for the study interruption. As for the study duration (variable "End Study Date") the analysis will be presented in Table S.1 (see Section 9.1). The data will also be listed in Listing S.3 (Appendix 3).

## 9 DESCRIPTION OF THE STATISTICAL REPORT AND GENERAL FORMAT OF TFLS

### 9.1 Presentation of the Data

Tables and listings will be produced in accordance with the principles outlined by the ICH E3 guideline "Note for Guidance on Structure and Content of Clinical Study Report" (CPMP/ICH/137/95).

Quantitative variables will be summarized using the SAS UNIVARIATE or SUMMARY procedures.

Categorical variables will be summarized using the SAS FREQ procedure.

Tables and listings will be produced in accordance with the principles outlined by the ICH E3 guideline and numbered as follows (where n is a sequential number):

	
e-CIG VS. IQOS Statistical Analysis Plan Version 2.0
	Doc code: BIOSTAT.SAP.02
		Pag. 18 of 115

- ✓ Table D.n/Listing Dn for the Baseline characteristics and data collected during the visits other than the Safety ones;
- ✓ Table E.n for the Efficacy data (the Efficacy data will be listed in one of the other three set of listings);
- ✓ Table S.n/Listing S.n for the Safety data.

## 9.2 Tables, Graphs and Listings Layout

The statistical analyses will be performed by the Biostatistician in charge in Fullcro S.r.l.. All tables, figures and listings of the Statistical Report will be generated using the software package SAS® Ver. 9.4.

As for the format of the SAS® outputs (tables and listings), all the pages will contain the following information:

- ✓ Protocol identification.
- ✓ Name of the Sponsor.
- ✓ Specification of document version.
- ✓ Date when the output was generated.

In addition, the following recommendations shall be fulfilled:

- ✓ titles should be fully explicative for the content of the tables/listings;
- ✓ all abbreviations used in any part of the output must be defined in footnotes.

As for character and spacing of the SAS® outputs, the following recommendations shall be fulfilled:

- ✓ SAS Monospace, Size: 8 or 7 (7 or 6 for listings);
- ✓ Margins (for both vertical and horizontal outputs):
  - Upper 2.5 cm;
  - Lower 1.0 cm;
  - Left 2.5 cm;
  - Right 1.0 cm.

Post-text tables and post-text listings will be included as appendices in the SR.

The post-text tables will be numbered according to presented in the list included in Appendix 1.

The rule for numbering the post-text listings will be as for post-text tables, but a prefix PL will be added.

### 9.3 General Description of the Statistical Report (SR)

The Statistical Report (SR) of this study will follow the recommendations given in the guideline ICH topic E3.

American English will be used for writing the SR.

The core of the SR will be written with Microsoft Word®; all data summaries (tables) and listings will be prepared by using SAS® Version 9.4. In-text tables will be generated with Word. A complete list of the in-text tables is not provided in this document. However, the standard format of these tables must be compliant with the sample illustrated below.

Panel 1: Sample of in-text tables

Table # Sample of in-text tables

Variable	Group HnC	Group EC
Continuous variable (unit):		
N	xx	xx
Missing	xx	xx
Mean (SD)	xx.x (xx.x)	xx.x (xx.x)
Median	xx.x	xx.x
Q1 – Q3	xx.x – xx.x	xx.x – xx.x
Categorical variable – n (%):		
Class 1	xx (xx.x)	xx (xx.x)
Class 2	xx (xx.x)	xx (xx.x)
...		
Class k	xx (xx.x)	xx (xx.x)

Source: Post-text table # and/or listing #

It is mandatory that every in-text table be cross-referenced with the corresponding post-text tables and listings. In addition, the titles must be auto-explicative and all acronyms must be described in footnotes. When relevant, the time of assessment must be specified.

### 9.4 Responsibilities

The SR of the present study will be written by the Biostatistician in charge in Fullcro S.r.l. and approved by the Sponsor's representative.

	e-CIG VS. IQOS Statistical Analysis Plan Version 2.0	Doc code: BIOSTAT.SAP.02
		Pag. 20 of 115

## 9.5 Structure of the Statistical Report

The SR will be divided in sections, titled and numbered.

## 9.6 Format of the Statistical Report

All the pages of the SR core (text) should contain the following information:

- ✓ Protocol identification;
- ✓ Page number;
- ✓ Name of the Sponsor;
- ✓ Specification of document version and date;
- ✓ Information on the level of restriction.

As for character and spacing of the SR core (text), the following recommendations shall be fulfilled:

- ✓ Century Gothic (type size 10);
- ✓ Line spacing 1.5;
- ✓ Justified;
- ✓ Margins as for vertical format:
  - Upper 4.0 cm;
  - Lower 4.2 cm;
  - Left 2.5 cm;
  - Right 2.0 cm.
- ✓ Margins as for horizontal format:
- ✓ Upper 3.5 cm;
- ✓ Lower 2.0 cm;
- ✓ Left 4.2 cm;
- ✓ Right 4.0 cm.
- ✓ Header 2.0 cm (from upper edge of page);
- ✓ Footer 2.5 cm (from lower edge of page).

## 9.7 Decision taken during the DRM

As described in the Minute included in Appendix 5, on the 10th June 2020 the Data Review Meeting of the study was held in call conference manner. All the decision taken were reported in the Minute. The main decision regarded the analysis population definition. All the protocol violations were evaluated, therefore the following populations were approved by the team:

Population **Safety**: 220

	e-CIG VS. IQOS Statistical Analysis Plan Version 2.0	Doc code: BIOSTAT.SAP.02
		Pag. 21 of 115

Population **Intention-To-Treat**: 217

Population **Per-Protocol**: 193

Population **Per-Protocol V7**: 177

## 10 APPENDIX

- Appendix 1 List of TLFs
- Appendix 2 Mock Tables: Tables
- Appendix 3 Mock Table: Listings
- Appendix 4 Study Flow Chart
- Appendix 5 DRM Minute

e-CIG VS. IQOS  
Statistical Analysis Plan  
Version 2.0

Doc code:  
BIOSTAT.SAP.02

Pag. 22 of 115

**APPENDIX 1**  
**List of Tables/Listings to be generated for the Statistical Report**

Table number	Baseline Characteristics - Table title
Table D.1	Patients Accountability by group
Table D.2a	Summary of Demographic and Screening/Baseline Characteristics by group
Table D.2b	Summary of Smoking Information at Screening/Baseline by group
Table D.3	Summary of Past Medical History by group
Table D.4a	Summary of Present Medical History by group
Table D.4b	Summary of Present Medical History Not in Treatment by group
Table D.4c	Summary of Present Medical History in Treatment by group
Table D.5	Summary of Patients' Characteristics/Vital Signs at Screening/Baseline by group
Table D.6	Summary of Urine Collection And Storage at Screening/Baseline by group
Table D.7	Summary of Fagerstrom test for nicotine dependence by group
Table D.8	Summary of Step Test at Baseline by group

Table number	Efficacy Analyses - Table title
Table E.1a	Summary of the Primary End-point. Quit Rate at all visites
Table E.1b	Summary of the Primary End-point: Quit Rate at final visit comparison
Table E.2	Summary of the Secondary End-point. Smoking reduction derived from the use of HnB and EC at week 12
Table E.3	Summary of the Secondary End-point. Adoption rate and adherence to product use at week 12
Table E.4a1	Summary of the Secondary End-point. mCEQ Questionnaire (scores) by visit
Table E.4a2	Summary of the Secondary End-point. mCEQ Questionnaire. Inferential analysis on the mean changes at final visit from baseline
Table E.4b1	Summary of the Secondary End-point. Smoking Cue Appeal Questionnaire (questions) by visit
Table E.4b2	Summary of the Secondary End-point. Smoking Cue Appeal Questionnaire. Inferential analysis on the mean changes at final visit from baseline
Table E.4c2	Summary of the Secondary End-point. ITUQ Questionnaire. Inferential analysis on the mean changes at final visit from baseline
Table E.4d1	Summary of the Secondary End-point. Risk Perception (PRI-P CC) Questionnaire (scores) by visit
Table E.4d2	Summary of the Secondary End-point. Risk Perception (PRI-P CC). Inferential analysis on the mean changes at final visit from baseline
Table E.4e1	Summary of the Secondary End-point. Risk Perception (PRI-P RRP) Questionnaire (scores) by visit

Table E.4e2	Summary of the Secondary End-point. Risk Perception (PRI-P RRP) Questionnaire. Inferential analysis on the mean changes at final visit from baseline
Table E.4f	Summary of the Secondary End-point. Device delivery by group
Table E.5	Summary of the Secondary Endpoint. Biomarkers of Biological Exposure (BoBE) - eCO (ppm)
Table E.6	Summary of the Secondary Endpoint. EQ-5D questionnaire
Table E.7a	Summary of the Secondary Endpoint. Step test by visit
Table E.7b	Step test – inferential analysis of VO2MAX

Table number	Safety Analyses - Table title
Table S.1	Summary of Extent of Exposure and Compliance by group
Table S.2	Summary of AEs by group
Table S.3	Summary of Vital Signs by Visit
Table S.4	Summary of End Study Information

Listing number	Listing title
Listing D.1	Patients' Disposition
Listing D.2	Eligibility: Inclusion Criteria
Listing D.3	Eligibility: Exclusion Criteria
Listing D.4a	Demographic Data
Listing D.4b	Smoking Information
Listing D.5	Past and Present Medical History
Listing D.6	Urine collection and Storage
Listing D.7	Fagerstrom test for nicotine dependence
Listing D.8	Step Test

Listing D.9	Device Consignment
Listing D.10	Product use recording
Listing E.1	EQ-5D
Listing E.2	mCE Questionnaire
Listing E.3	Smoking Cue Appeal Questionnaire
Listing E.4	ITUQ Questionnaire
Listing E.5	Risk Perception (PRI-P CC) Questionnaire
Listing E.6	Risk Perception (PRI-P RRP) Questionnaire
Listing S.1	Extent of Exposure and Study Duration
Listing S.2	Adverse Events
Listing S.3	Vital Signs

	e-CIG VS. IQOS Statistical Analysis Plan Version 2.0	Doc code: BIOSTAT.SAP.02
		Pag. 26 of 115

**APPENDIX 2**  
**Mock tables: Tables**

	e-CIG VS. IQOS Statistical Analysis Plan Version 2.0	Doc code: BIOSTAT.SAP.02
		Pag. 27 of 115

## **BASELINE CHARACTERISTICS**

Sponsor: Center for Tobacco Research, Cessation and Prevention, [name]  
Protocol: Progetto e-cig vs IQOS

Table D.1 Patients Accountability by group  
Population: All enrolled subjects

	Group HnB	Group EC
Enrolled	XXXX (XX.X%)	XXXX (XX.X%)
Screening failures	XXXX (XX.X%)	XXXX (XX.X%)
Safety	XXXX (XX.X%)	XXXX (XX.X%)
Intention-To-Treat	XXXX (XX.X%)	XXXX (XX.X%)
Reason for withdrawal:		
Reason 1	XX (XX.X%)	XX (XX.X%)
Reason 2	XX (XX.X%)	XX (XX.X%)
Reason 3	XX (XX.X%)	XX (XX.X%)

Sponsor: Center for Tobacco Research, Cessation and Prevention, [name]  
Protocol: Progetto e-cig vs IQOS

Table D.2a Summary of Demographic and Screening/Baseline Characteristics by group  
Population: Safety

		Group HnB	Group EC
		N=XXXX	N=XXXX
Age at the time of IC Signature Date	N	XX	XX
	N missing	XX	XX
	Mean	XX.X	XX.X
	Std. deviation	XX.X	XX.X
	Median	XX.X	XX.X
	Q1-Q3	X.X - XX.X	X.X - XX.X
Gender at birth	Male	XX (XX.X%)	XX (XX.X%)
	Female	XX (XX.X%)	XX (XX.X%)
Education	Primary School	XX (XX.X%)	XX (XX.X%)
	Secondary School	XX (XX.X%)	XX (XX.X%)
	High School	XX (XX.X%)	XX (XX.X%)
	University	XX (XX.X%)	XX (XX.X%)

Sponsor: Center for Tobacco Research, Cessation and Prevention, [name]  
Protocol: Progetto e-cig vs IQOS

Table D.2b Summary of Smoking Information at Screening/Baseline by group (1 of 2)  
Population: Safety

		Group HnB	Group EC
		N=XXXX	N=XXXX
N. cigarettes/die Screening	N	XX	XX
	N missing	XX	XX
	Mean	XX.X	XX.X
	Std. deviation	XX.X	XX.X
	Median	XX.X	XX.X
	Q1-Q3	X.X - XX.X	X.X - XX.X
How long has the subject smoked at least 10 cigarettes/die? (years)	N	XX	XX
	N missing	XX	XX
	Mean	XX.X	XX.X
	Std. deviation	XX.X	XX.X
	Median	XX.X	XX.X
	Q1-Q3	X.X - XX.X	X.X - XX.X
Years of Smoking (years)	N	XX	XX
	N missing	XX	XX
	Mean	XX.X	XX.X
	Std. deviation	XX.X	XX.X
	Median	XX.X	XX.X
	Q1-Q3	X.X - XX.X	X.X - XX.X
N. of quit attempts	N	XX	XX
	N missing	XX	XX
	Mean	XX.X	XX.X
	Std. deviation	XX.X	XX.X
	Median	XX.X	XX.X
	Q1-Q3	X.X - XX.X	X.X - XX.X
Exhaled breath Carbon monoxide (eCO) Screening (ppm)	N	XX	XX
	N missing	XX	XX
	Mean	XX.X	XX.X
	Std. deviation	XX.X	XX.X
	Median	XX.X	XX.X
	Q1-Q3	X.X - XX.X	X.X - XX.X

<File: [..]\Work\_In\_Progress\[..]\Statistica\Programmi\xxxxx.sas>  
<Source: [..]\Work\_In\_Progress\[..]\Gestione Dati\Dati SAS\xxxxx.sas7bdat>  
For further information see Listing D.5

Generated on XXXXXXXXXX XX:XX

Sponsor: Center for Tobacco Research, Cessation and Prevention, [name]  
Protocol: Progetto e-cig vs IQOS

Table D.2b Summary of Smoking Information at Screening/Baseline by group (2 of 2)  
Population: Safety

		Group HnB	Group EC
		N=XXXX	N=XXXX
Brand of used cigarettes	Brand#1	XX (XX.X%)	XX (XX.X%)
	Brand#2	XX (XX.X%)	XX (XX.X%)
	. . . . .		
	Brand#n	XX (XX.X%)	XX (XX.X%)

Sponsor: Center for Tobacco Research, Cessation and Prevention, [name]  
Treatment: HnB vs EC

Table D.3 Summary of Past Medical History by group  
Population: Safety

System Organ Class	Preferred Term	Group HnB	Group EC
		N=XXXX	N=XXXX
SOC #1	TOTAL	XX (XX.X%)	XX (XX.X%)
	PREFERRED TERM #1	XX (XX.X%)	XX (XX.X%)
	PREFERRED TERM #2	XX (XX.X%)	XX (XX.X%)
	. . . . .		
	PREFERRED TERM #n	XX (XX.X%)	XX (XX.X%)
SOC #2	TOTAL	XX (XX.X%)	XX (XX.X%)
	PREFERRED TERM #1	XX (XX.X%)	XX (XX.X%)
	PREFERRED TERM #2	XX (XX.X%)	XX (XX.X%)
	. . . . .		
	PREFERRED TERM #n	XX (XX.X%)	XX (XX.X%)
. . . . .	TOTAL	XX (XX.X%)	XX (XX.X%)
	PREFERRED TERM #1	XX (XX.X%)	XX (XX.X%)
	PREFERRED TERM #2	XX (XX.X%)	XX (XX.X%)
	. . . . .		
	PREFERRED TERM #n	XX (XX.X%)	XX (XX.X%)
SOC #n	TOTAL	XX (XX.X%)	XX (XX.X%)
	PREFERRED TERM #1	XX (XX.X%)	XX (XX.X%)
	PREFERRED TERM #2	XX (XX.X%)	XX (XX.X%)
	. . . . .		
	PREFERRED TERM #n	XX (XX.X%)	XX (XX.X%)

<File: [..]\Work\_In\_Progress\[..]\Statistica\Programmi\xxxxx.sas>  
<Source: [..]\Work\_In\_Progress\[..]\Gestione Dati\Dati SAS\xxxxx.sas7bdat>      Generated on XXXXXXXXXX XX:XX  
The percentages are computed considering the total of the past medical history abnormalities by group  
Coded using MedDRA dictionary (<last available version>)  
For further information see Listing X.X

Sponsor: Center for Tobacco Research, Cessation and Prevention, [name]  
Protocol: Progetto e-cig vs IQOS

Table D.4a Summary of Present Medical History by group  
Population: Safety

System Organ Class	Preferred Term	Group HnB	Group EC
		N=XXXX	N=XXXX
SOC #1	TOTAL	XX (XX.X%)	XX (XX.X%)
	PREFERRED TERM #1	XX (XX.X%)	XX (XX.X%)
	PREFERRED TERM #2	XX (XX.X%)	XX (XX.X%)
	. . . . .		
	PREFERRED TERM #n	XX (XX.X%)	XX (XX.X%)
SOC #2	TOTAL	XX (XX.X%)	XX (XX.X%)
	PREFERRED TERM #1	XX (XX.X%)	XX (XX.X%)
	PREFERRED TERM #2	XX (XX.X%)	XX (XX.X%)
	. . . . .		
	PREFERRED TERM #n	XX (XX.X%)	XX (XX.X%)
. . . . .	TOTAL	XX (XX.X%)	XX (XX.X%)
	PREFERRED TERM #1	XX (XX.X%)	XX (XX.X%)
	PREFERRED TERM #2	XX (XX.X%)	XX (XX.X%)
	. . . . .		
	PREFERRED TERM #n	XX (XX.X%)	XX (XX.X%)
SOC #n	TOTAL	XX (XX.X%)	XX (XX.X%)
	PREFERRED TERM #1	XX (XX.X%)	XX (XX.X%)
	PREFERRED TERM #2	XX (XX.X%)	XX (XX.X%)
	. . . . .		
	PREFERRED TERM #n	XX (XX.X%)	XX (XX.X%)

<File: [..]\Work\_In\_Progress\[..]\Statistica\Programmi\xxxxx.sas>  
<Source: [..]\Work\_In\_Progress\[..]\Gestione Dati\Dati SAS\xxxxx.sas7bdat>      Generated on XXXXXXXXXX XX:XX  
The percentages are computed considering the total of the current medical history abnormalities by group  
Coded using MedDRA dictionary (<last available version>)  
For further information see Listing X.X

Sponsor: Center for Tobacco Research, Cessation and Prevention, [name]  
Protocol: Progetto e-cig vs IQOS

Table D.4b Summary of Present Medical History not in Treatment by group  
Population: Safety

System Organ Class	Preferred Term	Group HnB	Group EC
		N=XXXX	N=XXXX
SOC #1	TOTAL	XX (XX.X%)	XX (XX.X%)
	PREFERRED TERM #1	XX (XX.X%)	XX (XX.X%)
	PREFERRED TERM #2	XX (XX.X%)	XX (XX.X%)
	. . . . .		
	PREFERRED TERM #n	XX (XX.X%)	XX (XX.X%)
SOC #2	TOTAL	XX (XX.X%)	XX (XX.X%)
	PREFERRED TERM #1	XX (XX.X%)	XX (XX.X%)
	PREFERRED TERM #2	XX (XX.X%)	XX (XX.X%)
	. . . . .		
	PREFERRED TERM #n	XX (XX.X%)	XX (XX.X%)
. . . . .	TOTAL	XX (XX.X%)	XX (XX.X%)
	PREFERRED TERM #1	XX (XX.X%)	XX (XX.X%)
	PREFERRED TERM #2	XX (XX.X%)	XX (XX.X%)
	. . . . .		
	PREFERRED TERM #n	XX (XX.X%)	XX (XX.X%)
SOC #n	TOTAL	XX (XX.X%)	XX (XX.X%)
	PREFERRED TERM #1	XX (XX.X%)	XX (XX.X%)
	PREFERRED TERM #2	XX (XX.X%)	XX (XX.X%)
	. . . . .		
	PREFERRED TERM #n	XX (XX.X%)	XX (XX.X%)

Sponsor: Center for Tobacco Research, Cessation and Prevention, [name]  
 Protocol: Progetto e-cig vs IQOS

Table D.4c Summary of Present Medical History in Treatment by group  
 Population: Safety

System Organ Class	Preferred Term	Group HnB N=XXXX	Group EC N=XXXX
SOC #1	TOTAL	XX (XX.X%)	XX (XX.X%)
	PREFERRED TERM #1	XX (XX.X%)	XX (XX.X%)
	PREFERRED TERM #2	XX (XX.X%)	XX (XX.X%)
	. . . . .		
	PREFERRED TERM #n	XX (XX.X%)	XX (XX.X%)
SOC #2	TOTAL	XX (XX.X%)	XX (XX.X%)
	PREFERRED TERM #1	XX (XX.X%)	XX (XX.X%)
	PREFERRED TERM #2	XX (XX.X%)	XX (XX.X%)
	. . . . .		
	PREFERRED TERM #n	XX (XX.X%)	XX (XX.X%)
. . . . .	TOTAL	XX (XX.X%)	XX (XX.X%)
	PREFERRED TERM #1	XX (XX.X%)	XX (XX.X%)
	PREFERRED TERM #2	XX (XX.X%)	XX (XX.X%)
	. . . . .		
	PREFERRED TERM #n	XX (XX.X%)	XX (XX.X%)
SOC #n	TOTAL	XX (XX.X%)	XX (XX.X%)
	PREFERRED TERM #1	XX (XX.X%)	XX (XX.X%)
	PREFERRED TERM #2	XX (XX.X%)	XX (XX.X%)
	. . . . .		
	PREFERRED TERM #n	XX (XX.X%)	XX (XX.X%)

<File: [..]\Work\_In\_Progress\[..]\Statistica\Programmi\xxxxx.sas>  
 <Source: [..]\Work\_In\_Progress\[..]\Gestione Dati\Dati SAS\xxxxx.sas7bdat>      Generated on XXXXXXXX XX:XX  
 The percentages are computed considering the total of the current medical history abnormalities by group  
 Coded using MedDRA dictionary (<last available version>)  
 For further information see Listing X.X

Sponsor: Center for Tobacco Research, Cessation and Prevention, [name]  
Protocol: Progetto e-cig vs IQOS

Table D.5 Summary of Patients' Characteristics/Vital Signs at Baseline by group. (1 of n)  
Population: <Safety/Continuous Quitter>

Parameter	Statistic	Group HnB	Group EC
		N=XXXX	N=XXXX
Parameter #1	N	XX	XX
<um>	N missing	XX	XX
	Mean	XXX.X	XXX.X
	Std. deviation	XX.X	XX.X
	Median	XXX.X	XXX.X
	Q1-Q3	XX.X - XXX.X	XX.X - XXX.X
Parameter #2	N	XX	XX
<um>	N missing	XX	XX
	Mean	XXX.X	XXX.X
	Std. deviation	XX.X	XX.X
	Median	XXX.X	XXX.X
	Q1-Q3	XX.X - XXX.X	XX.X - XXX.X
. . . . .	N	XX	XX
<um>	N missing	XX	XX
	Mean	XXX.X	XXX.X
	Std. deviation	XX.X	XX.X
	Median	XXX.X	XXX.X
	Q1-Q3	XX.X - XXX.X	XX.X - XXX.X
Parameter #n	N	XX	XX
<um>	N missing	XX	XX
	Mean	XXX.X	XXX.X
	Std. deviation	XX.X	XX.X
	Median	XXX.X	XXX.X
	Q1-Q3	XX.X - XXX.X	XX.X - XXX.X

Sponsor: Center for Tobacco Research, Cessation and Prevention, [name]  
Protocol: Progetto e-cig vs IQOS

Table D.6 Summary of Urine Collection And Storage at Screening/Baseline by group  
Population: Safety

		Group HnB	Group EC
		N=XXXX	N=XXXX
Instruction for urine collection and storage given to the subject	Yes	XX (XX.X%)	XX (XX.X%)
	No	XX (XX.X%)	XX (XX.X%)
N. of unire containers Delivered	N	XX	XX
	N missing	XX	XX
	Mean	XX.X	XX.X
	Std. deviation	XX.X	XX.X
	Median	XX.X	XX.X
	Q1-Q3	XX.X - XXX.X	XX.X - XXX.X
Has the subject returned the urine to the center? (Baseline)	Yes	XX (XX.X%)	XX (XX.X%)
	No	XX (XX.X%)	XX (XX.X%)

Sponsor: Center for Tobacco Research, Cessation and Prevention, [name]  
Protocol: Progetto e-cig vs IQOS

Table D.7 Summary of Fagerstrom test for nicotine dependence by group  
Population: Safety

		Group HnB	Group EC
		N=XXXX	N=XXXX
Quanto tempo dopo il risveglio fuma la prima sigaretta?	Entro 5 min	XX (XX.X%)	XX (XX.X%)
	Dopo 6-30	XX (XX.X%)	XX (XX.X%)
	Dopo 31-60 min	XX (XX.X%)	XX (XX.X%)
	Dopo 60 min	XX (XX.X%)	XX (XX.X%)
Trova difficile non fumare nei luoghi dove è vietato?	Si	XX (XX.X%)	XX (XX.X%)
	No	XX (XX.X%)	XX (XX.X%)
A quale sigaretta farebbe più fatica a rinunciare?	Alla 1 ^ del mattino	XX (XX.X%)	XX (XX.X%)
	A qualsiasi altra	XX (XX.X%)	XX (XX.X%)
Quante sigarette fuma al giorno?	Più di 30	XX (XX.X%)	XX (XX.X%)
	21-30	XX (XX.X%)	XX (XX.X%)
	11-20	XX (XX.X%)	XX (XX.X%)
	10 o meno	XX (XX.X%)	XX (XX.X%)
Tende a fumare più spesso nelle prime ore dopo il risveglio che durante il resto del giorno?	Si	XX (XX.X%)	XX (XX.X%)
	No	XX (XX.X%)	XX (XX.X%)
Fuma anche se è malato e deve rimanere a letto la maggior parte del giorno?	Si	XX (XX.X%)	XX (XX.X%)
	No	XX (XX.X%)	XX (XX.X%)

<File: [..]\Work\_In\_Progress\[..]\Statistica\Programmi\xxxxx.sas>

<Source: [..]\Work\_In\_Progress\[..]\Gestione Dati\Dat SAS\xxxxx.sas7bdat>

Generated on XXXXXXXX XX:XX

For further information see Listing X.X

Sponsor: Center for Tobacco Research, Cessation and Prevention, [name]  
 Protocol: Progetto e-cig vs IQOS

Table D.8a Summary of Step Test, Step1 to Step 5, at Baseline by group  
 Population: Safety

		Group HnB		Group EC	
		Heart Rate	SpO2	Heart Rate	SpO2
Step 1	N	XX	XX	XX	XX
	N missing	XX	XX	XX	XX
	Mean	XX.X	XX.X	XX.X	XX.X
	Std. deviation	XX.X	XX.X	XX.X	XX.X
	Median	XX.X	XX.X	XX.X	XX.X
	Q1-Q3	X.X - XX.X	X.X - XX.X	X.X - XX.X	X.X - XX.X
. . . . .	N	XX	XX	XX	XX
	N missing	XX	XX	XX	XX
	Mean	XX.X	XX.X	XX.X	XX.X
	Std. deviation	XX.X	XX.X	XX.X	XX.X
	Median	XX.X	XX.X	XX.X	XX.X
	Q1-Q3	X.X - XX.X	X.X - XX.X	X.X - XX.X	X.X - XX.X
Step 5	N	XX	XX	XX	XX
	N missing	XX	XX	XX	XX
	Mean	XX.X	XX.X	XX.X	XX.X
	Std. deviation	XX.X	XX.X	XX.X	XX.X
	Median	XX.X	XX.X	XX.X	XX.X
	Q1-Q3	X.X - XX.X	X.X - XX.X	X.X - XX.X	X.X - XX.X

Sponsor: Center for Tobacco Research, Cessation and Prevention, [name]  
Protocol: Progetto e-cig vs IQOS

Table D.8b Summary of Step Test, other informations, at Baseline by group  
Population: Safety

		Group HnB		Group EC	
		Heart Rate	SpO2	Heart Rate	SpO2
Basal Condition	N	XX	XX	XX	XX
Recovery Time	N missing	XX	XX	XX	XX
(seconds)	Mean	XX.X	XX.X	XX.X	XX.X
	Std. deviation	XX.X	XX.X	XX.X	XX.X
	Median	XX.X	XX.X	XX.X	XX.X
	Q1-Q3	X.X - XX.X	X.X - XX.X	X.X - XX.X	X.X - XX.X
Stop Time	N	XX		XX	
	N missing	XX		XX	
	Mean	XX.X		XX.X	
	Std. deviation	XX.X		XX.X	
	Median	XX.X		XX.X	
	Q1-Q3	X.X - XX.X		X.X - XX.X	
VO2MAX	N	XX		XX	
	N missing	XX		XX	
	Mean	XX.X		XX.X	
	Std. deviation	XX.X		XX.X	
	Median	XX.X		XX.X	
	Q1-Q3	X.X - XX.X		X.X - XX.X	

	e-CIG VS. IQOS Statistical Analysis Plan Version 2.0	Doc code: BIOSTAT.SAP.02
		Pag. 41 of 115

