### **Inclusion criteria:**

Subjects must meet all of the following inclusion criteria to be eligible for enrolment into the study:

1. Able to comply with the study procedures

2. Male or female healthy smokers aged  $\geq 19$
3. Smoking at least 10 cigarettes a day
4. Smoking for at least one year
5. Not currently attempting to quit smoking or wishing to do so in the next 30 days (this will be verified at screening by the answer “NO” to both questions “Do you intend to quit in the next 30 days?” and “Are you interested in taking part in one of our smoking cessation programs?”)
6. Female smokers not planning to become pregnant are using an acceptable form of contraception.

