#### **Exclusion criteria:**

The presence of any of the following will exclude a subject from study enrolment:

1. Use of smokeless tobacco, or any other tobacco products (including e-cigarettes, cigars, chewing tobacco, snus, etc.) within the last 3 months, at baseline and during the whole study.
2. Use of nicotine replacement therapy or other smoking cessation therapies within the last 3 months and at baseline.
3. Self-reported pregnancy, planned pregnancy or breastfeeding.
4. Tobacco industry employees and 1st degree relatives will be excluded in order to safeguard independence of the study.

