### **6.4 Medical History**

The medical conditions will be coded with the MedDRA dictionary (last available version) and be analyzed as previous and present Medical History using the variable "Ongoing" for creating the two sets of data. The past and present incidence of the different conditions by system organ class and preferred term will be described with frequencies and percentages (Appendix 2: Tables D.3 and D.4a). Present Medical History is defined "In treatment" if the disease is still being treated at the time of the signing of the informed consent and "Not in treatment" otherwise. Present Medical History In treatment and Not in treatment will be summarized through further tables. (Appendix 2: Tables D.4b and D.4c)

These data will also be listed (Appendix 3: Listings D.6, D.7, D.8, D.9).

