## SAFETY ENDPOINTS

	e-CIG VS. IQOS Statistical Analysis Plan Version 2.0	Doc code: BIOSTAT.SAP.02
		Pag. 63 of 115

Sponsor: Center for Tobacco Research, Cessation and Prevention, [name]  
Protocol: Progetto e-cig vs IQOS

Table S.1 Summary of Extent of Exposure by group  
Population: Safety

		Group HnB	Group EC
		N=XXX	N=XXX
Extent of Exposure	N	XX	XX
	N missing	XX	XX
	Mean	XX.X	XX.X
	Std. deviation	XX.X	XX.X
	Median	XX.X	XX.X
	Q1-Q3	XX.X - XX.X	XX.X - XX.X

---

<File: [..]\Work\_In\_Progress\[..]\Statistica\Programmi\xxxxx.sas>  
<Source: [..]\Work\_In\_Progress\[..]\Gestione Dati\Dati SAS\xxxxx.sas7bdat>      Generated on XXXXXXXXXX XX:XX  
The Extent of exposure is computed as (Visit 6 date - Baseline date)  
For further information see Listing X.X

	e-CIG VS. IQOS Statistical Analysis Plan Version 2.0	Doc code: BIOSTAT.SAP.02
		Pag. 64 of 115

Sponsor: Center for Tobacco Research, Cessation and Prevention, [name]  
Protocol: Progetto e-cig vs IQOS

Table S.2 Summary of Adverse Drug Reactions by group  
Population: Safety

	Group HnB N=XXX	Group EC N=XXX
ADRs	XX (XX.X%)	XX (XX.X%)
SADRs	XX (XX.X%)	XX (XX.X%)
Related ADRs	XX (XX.X%)	XX (XX.X%)

<File: [..]\Work\_In\_Progress\[..]\Statistica\Programmi\xxxxx.sas>  
<Source: [..]\Work\_In\_Progress\[..]\Gestione Dati\Dati SAS\xxxxx.sas7bdat>

Generated on XXXXXXXXXX XX:XX

The percentages are calculated on the total of the enrolled patients by group  
ADRS classified as Possible/Probably/Definite are considered as Related ADRS  
For further information see Listing X.X

e-CIG VS. IQOS  
Statistical Analysis Plan  
Version 2.0

Doc code:  
BIOSTAT.SAP.02

Pag. 65 of 115

Sponsor: Center for Tobacco Research, Cessation and Prevention, [name]  
Protocol: Progetto e-cig vs IQOS

Table S.3 Summary of Vital Signs by group < Group HnB / Group EC >  
Population: <Safety/Continuous Quitters>

Parameter <Unit>	Visit	Observed Values at Visit							Changes From Visit 1 to Visits 6 and 7						
		N	N miss	Mean	STD	CI 95%	Median	Range (Q1-Q3)	N	N miss	Mean	STD	CI 95%	Median	Range (Q1-Q3)
parameter #1 <um>	Baseline	XX	XX	XX.XX	XX.XX	[XX.XX,XXX.X]	XX.XX	(XX.XX - XXX.X)							
	Visit 2	XX	XX	XX.XX	XX.XX	[XX.XX,XXX.X]	XX.XX	(XX.XX - XXX.X)							
	. . . . . Follow-up	XX	XX	XX.XX	XX.XX	[XX.XX,XXX.X]	XX.XX	(XX.XX - XXX.X)	XX	XX	XX.XX	XX.XX	[XX.XX,XXX.X]	XX.XX	(XX.XX - XXX.X)

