XXXXXX	XXXXXX	XX/XXXX	X	X	X	X
XXXXXX	XXXXXX	XX/XXXX	X	X	X	X
XXXXXX	XXXXXX	XX/XXXX	X	X	X	X

<File: [..]\Work\_In\_Progress\[..]\Statistica\Programmi\xxxxx.sas>

<Source: [..]\Work\_In\_Progress\[..]\Gestione Dati\Dati SAS\xxxxx.sas7bdat>

Generated on XXXXXXXX XX:XX

Excl.Crit.#1: Use of smokeless tobacco, or any other tobacco products (including e-cigarettes, cigars, chewing tobacco, snus, etc.) within the last 3 months, at baseline and during the whole study;

Excl.Crit.#2: Use of nicotine replacement therapy or other smoking cessation therapies within the last 3 months and at baseline;

Excl.Crit.#3: Self-reported pregnancy, planned pregnancy or breastfeeding;

Excl.Crit.#4: Tobacco industry employees and 1st degree relatives will be excluded in order to safeguard independence of the study.

<Ordered by: Screening Number>

<Stratified by: Group>

Sponsor: Center for Tobacco Research, Cessation and Prevention, [name]  
Protocol: Progetto e-cig vs IQOS

Listing D.4b Smoking information < Group HnB / Group EC >

Screening Number	Random. Number	Age/Gender	How long smoked at least 10 cigarettes/die (years)	Brand of used cigarettes	Years of smoking	Number of quit attempts	Visit	Number of cigarette/die	Exhaled breath Carbon monoxide
XXXXXX	XXXXXX	XX/XXXX	XX	XXXXXXXXXX	XX	XX	XXXXXX XXXXXX XXXXXX XXXXXX XXXXXX XXXXXX XXXXXX	XX XX XX XX XX XX XX	XXX XXX XXX XXX XXX XXX XXX
XXXXXX	XXXXXX	XX/XXXX	XX	XXXXXXXXXX	XX	XX	XXXXXX XXXXXX XXXXXX XXXXXX XXXXXX XXXXXX XXXXXX	XX XX XX XX XX XX XX	XXX XXX XXX XXX XXX XXX XXX
XXXXXX	XXXXXX	XX/XXXX	XX	XXXXXXXXXX	XX	XX	XXXXXX XXXXXX XXXXXX XXXXXX XXXXXX XXXXXX XXXXXX	XX XX XX XX XX XX XX	XXX XXX XXX XXX XXX XXX XXX

---

<File: [..]\Work\_In\_Progress\[..]\Statistica\Programmi\xxxxx.sas>  
<Source: [..]\Work\_In\_Progress\[..]\Gestione Dati\Dati SAS\xxxxx.sas7bdat>      Generated on XXXXXXXXXX XX:XX

<Ordered by: Screening Number>  
<Stratified by: Group>

Sponsor: Center for Tobacco Research, Cessation and Prevention, [name]  
 Protocol: Progetto e-cig vs IQOS

Listing D.5 Past and Present Medical History < Group HnB / Group EC >

Screening Number	Random. Number	Age/Gender	Date of Visit	Description	Date of Onset	Date Resolved	Ongoing (Y/N)	Comment
XXXXXX	XXXXXX	XX/XXXX	XX/XX/XXXX	XXXXXXXXXX	XX/XX/XXXX	XX/XX/XXXX	X	XXXXXXXXXX
XXXXXX	XXXXXX	XX/XXXX	XX/XX/XXXX	XXXXXXXXXX	XX/XX/XXXX	XX/XX/XXXX	X	XXXXXXXXXX

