#### **2.6 Consistenza delle codifiche dei termini medici**

Il listato delle codifiche dei termini medici (solo Eventi Avversi) è stato inviato dallo Statistico al Team il 5 Giugno. A parte il termine non codificato (vedi Sezione 2.1) non è stata segnalata nessuna inconsistenza.

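### Minor: SAP Tables D.3, D.4a and D.4c take percentages of recorded conditions, not of participants, so they do not give the incidence that SAP 6.4 announces

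*SAP*

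**What the plan says.** SAP 6.4 (Medical History) sets the purpose of the tables: "The past and present incidence of the different conditions by system organ class and preferred term will be described with frequencies and percentages". It defines neither the counting unit nor the denominator.

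The mock tables in SAP Appendix 2 supply the denominator. The footnote of Table D.3 reads "The percentages are computed considering the total of the past medical history abnormalities by group". Tables D.4a and D.4c carry the parallel sentence: "The percentages are computed considering the total of the current medical history abnormalities by group". Table D.4b shows no footnote in the text available to me, so its base is not stated there.

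All four tables name the Safety population and print its N above each arm. Each cell holds a count and a percentage. The rows are a total for each SOC and one row per preferred term (PT). No row gives the number of participants with any condition.

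Table S.2, among the safety tables, uses a different base: "The percentages are calculated on the total of the enrolled patients by group".

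At subject level, Appendix 3 has "Listing D.5 Past and Present Medical History < Group HnB / Group EC >", with description, onset date, resolution date, an ongoing flag and a comment.

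**The concern.** A baseline medical-history table should tell the reader what proportion of each arm had a given condition, and whether the arms were alike. The word 'incidence' in SAP 6.4 and the Safety N in the column heads both point to participants as the base. The footnotes replace that base with the number of abnormalities in the arm, which is an outcome of data collection and differs between arms.

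Two things are lost. The percentages can no longer be set side by side across arms. And the simplest summary of the sample's health, how many participants had any past, present or treated condition, does not appear in the tables and cannot be built from them. That summary is of some interest here. The protocol describes the population as healthy (inclusion criterion 2: "Male or female healthy smokers aged") without defining the term. Blood pressure, heart rate, the step test and EQ-5D, all of which can depend on underlying illness, are among the outcomes.

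**Working it through.** The plan gives no figure on this point, so there is nothing to reproduce. The check is a reading of the footnotes plus arithmetic on assumed counts.

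**Inputs**

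- Base of the printed percentage, *A*: all past abnormalities in the arm (D.3 footnote), or all current abnormalities in the arm (D.4a and D.4c footnotes).
- Participants per arm, *N*: 110, the planned arm size (Protocol, Sample size calculation). SAP 9.7 gives a Safety population of 220 in total but no split by arm, so 110 is an assumption.
- Numbers of conditions: not in the documents. Every count below is assumed.

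**Step 1: what is printed.** For a PT recorded once in each of *c* participants:

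- printed percentage = *c* / *A*
- incidence among participants = *c* / *N*
- ratio of the two = *N* / *A*

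The ratio depends on the arm's own *A*. It is above 1 when there are fewer abnormalities than participants, and below 1 when there are more.

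**Step 2: unequal incidence, equal percentages.**

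| | *c* | *A* | Printed | Of 110 participants |
|---|---|---|---|---|
| Arm 1 | 10 | 30 | 10/30 = 33.3% | 10/110 = 9.1% |
| Arm 2 | 20 | 60 | 20/60 = 33.3% | 20/110 = 18.2% |

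The ratio is 110/30 = 3.67 in arm 1 and 110/60 = 1.83 in arm 2. The cells would read 10 (33.3%) and 20 (33.3%). The percentages agree; the counts do not.

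**Step 3: equal incidence, unequal percentages.** Keep the same totals and put 10 affected participants in each arm. The tables print 10/30 = 33.3% and 10/60 = 16.7%, while both arms have 9.1% affected.

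**Step 4: participants with any condition.** Suppose an arm has two PTs in different SOCs, each with a count of 22, so *A* = 44 and each prints 22/44 = 50.0%. The same cells arise from:

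- 44 participants with one condition each: 44/110 = 40.0% affected;
- 22 participants with both conditions: 22/110 = 20.0% affected.

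Nothing in the table separates the two cases. More generally, if no one has more than 5 conditions (an assumption), 50 abnormalities can come from 50/5 = 10 participants up to 50, that is 9.1% to 45.5% of 110.

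**Step 5: does the counting unit matter?** The SAP does not say whether a cell counts conditions or participants, although the base suggests conditions. If conditions, the number of participants affected within an SOC cannot be recovered, because one person may contribute several. If participants, the SOC counts are usable one at a time but still cannot be added across SOCs, because one person may appear under several. The number with any condition is missing either way.

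**The case against.** The strongest reply is that the tables disclose their base and print the count beside each percentage under a known N. For a PT recorded once per person, a reader can divide the count by N. That stands, and it limits the point: someone looking at Step 2 might infer that a twofold imbalance would be hidden, but 10 against 20 under equal column totals would be visible. It does not rescue the percentages as incidences, the SOC totals if cells count conditions, or the missing figure for any condition.

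Four stronger readings are tempting, and the documents do not support them.

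- *Health and balance can be judged only from these tables.* Listing D.5 gives conditions and the ongoing flag by subject, so participants with a present condition can be counted from it, though treatment status cannot. Baseline vital signs are in Table D.5, the step test and VO2MAX in Tables D.8a and D.8b, and EQ-5D at Visit 1 in Table E.6.
- *No entry criterion concerns health.* The exclusion list opens with "The presence of any of the following will exclude a subject from study enrolment" and its four items name no disease. But inclusion criterion 2 requires healthy smokers, every inclusion criterion must be met, and Listing D.2 records each one by participant. What is true is that 'healthy' has no operational definition. That is a separate protocol matter, which a table denominator does not cure.
- *Medical history will not be coded.* SAP 5.2 names a coded dataset only for adverse events, and section 2.6 of the Data Review Meeting minute covers an adverse-event coding list only. But SAP 6.4 commits to MedDRA coding of medical conditions, the footnotes of D.3, D.4a and D.4c repeat it, and SAP 5.2 leaves room for further derived datasets.
- *The report should stop calling the population healthy.* That is a reporting preference, and it sits badly with inclusion criterion 2.

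It is also fair to say that these tables are descriptive and feed no test and no analysis population. That settles the severity, not the correctness.

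**Conclusion.** The stated rule is wrong for its stated purpose, and the consequence is minor. Followed as written, Tables D.3, D.4a and D.4c print shares of recorded conditions where SAP 6.4 announces incidence. The percentages are not comparable between arms whose abnormality totals differ, and the number of participants with any condition cannot be read from the tables.

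The size cannot be stated for this trial because the condition counts are not in the documents. The distortion in a single-PT percentage is the factor *N*/*A* for each arm. The worked figures assume 110 participants per arm and invented counts, and they show only that equal percentages can accompany 9.1% and 18.2% affected, and the reverse. No imbalance is shown or implied. The primary non-inferiority comparison is untouched.

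**What to change.** In Tables D.3, D.4a and D.4c:

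1. Count each participant once per SOC and once per PT, and say so in the footnote.
2. Divide by the Safety N of the arm, as already printed in the column head, and replace the present footnote on the base.
3. Add a first row to each table for participants with at least one condition of the kind tabulated (past, present, or present and in treatment).

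State the same counting rule and base for Table D.4b, and add the row there too for present conditions not in treatment.

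The cost is a changed denominator and one added row in up to four table programs, on data already collected. No participant, visit or analysis population is affected. If the SAP is not reissued, the change can be recorded in the Statistical Report as a deviation, which SAP section 1 already provides for.
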